5.8. Other Analyses

5.8.1. Reactogenicity

For all participants in the safety subset the diary data will be summarized descriptively by treatment group. Temperature will be summarized using the maximum of the recorded temperature per subject by study day, and summarizing incidences of fever using the highest grade of fever observed for each subject using the grading system in Appendix 6. The same approach will be taken for the maximum size of any swelling. All symptoms will be summarized taking the worst grading as captured by the investigator at the Day 28 visit. For all symptoms also incidences of worst gradings will be summarized by Day comparing treatment groups.

5.8.2. Immunogenicity

Blood will be collected from all non-Immuno Subset participants for humoral immunogenicity assessments before double-blind vaccination, 28 days after double-blind vaccination and at D71, W24 and W782 after double-blind vaccination. For a total of approximately 400 participants in the Immuno Subset, blood will be collected for analysis of humoral immune responses before double-blind vaccination, 28 days after double-blind vaccination, 70 days after double-blind vaccination, and 24, 52, 78, and 104 weeks after double-blind vaccination.

During a COVID-19 episode, blood will be collected on COVID-19 Day 3-5 and on COVID-19 Day 29 for immunogenicity assessments, including the assays summarized in [Table 9](#).

Table 9 Immunogenicity and Transcriptomic Assessments

Humoral Assays	Purpose
Supportive of Secondary Objectives	
SARS-CoV-2 binding antibodies to S protein (ELISA)	Analysis of antibodies binding to SARS-CoV-2 S protein
SARS-CoV-2 seroconversion based on antibodies to N protein (ELISA and/or SARS-CoV-2 immunoglobulin assay)	Analysis of antibodies binding to SARS-CoV-2 N protein
Supportive of Exploratory Objectives	
SARS-CoV-2 neutralization (VNA)	Analysis of neutralizing antibodies to the wild-type virus, and/or pseudovirion expressing S protein
SARS-CoV-2 binding antibodies to S protein (MSD)	Analysis of antibodies binding to SARS-CoV-2 S protein (different than the assays supportive of the secondary objectives) and the receptor-binding domain (RBD) of SARS-CoV-2 S protein
Functional and molecular antibody characterization	Analysis of antibody characteristics including, but not limited to, avidity, Fc-mediated viral clearance, Fc characteristics, Ig subclass, IgG isotype, antibody glycosylation, and assessment of antibody repertoire
Adenovirus neutralization (VNA)	Adenovirus neutralization assay to evaluate neutralizing antibody responses against the Ad26 vector
Binding antibodies to other coronaviruses (MSD)	Analysis of antibodies binding to coronaviruses other than SARS-CoV-2
Transcriptomic Assay	Purpose
Supportive of Exploratory Objectives	
Gene expression analysis	Analysis of gene expression by RNA transcript profiling in unstimulated cells or whole blood

Ad26 = adenovirus type 26; ELISA = enzyme-linked immunosorbent assay; Fc = crystallizable fragment; Ig(G) = immunoglobulin (G); MSD = Meso Scale Discovery; N = nucleocapsid; RBD = receptor-binding domain; RNA = ribonucleic acid; S = spike; SARS-CoV-2 = severe acute respiratory syndrome coronavirus-2; VNA = virus neutralization assay.

The analysis of immunogenicity will use the PPI set.

For the non-immuno subset, humoral immunogenicity data will be analyzed according to the as-treated principle by vaccine regimen (active vaccine, placebo), by vaccine regimen and participant seropositivity status at screening and by vaccine regimen and COVID-19 (no infection, asymptomatic infection, mild, at least mild, at least moderate, at least severe) and by vaccine regimen and age and

comorbidity (with/without) strata, by vaccine regimen and country/region, by vaccine regimen and emerging CD4 count abnormality (at least grade 1 at any time after double-blind vaccination) and viral load (treatment emergent detectable viral load). Specific immunogenicity analyses will be performed on the Immuno Subset. All immunogenicity analyses for the immuno subset will be analyzed by vaccine regimen and by vaccine regimen and age and comorbidity (with/without) strata.

At the time of primary analysis, partially available immunogenicity data are summarized. Analysis will be updated when complete data available.

For participants with a COVID-19 episode immunogenicity data will be analyzed by vaccine regimen at baseline, 28 days post double-blind vaccination, on COVID-19 Day 3-5 and on COVID-19 Day 29 for the standard immunogenicity assays (S-ELISA and VNA) and on COVID-19 Day 3-5 and on COVID-19 Day 29 for all other assays that are available (Table 6).

Correlates will be assessed in a subset where immune responses and transcriptome modifications are measured in all vaccine recipients who experience a SARS-CoV-2 event, and in random samples of vaccine recipients who have not been infected. These analyses will be described in a separate correlates SAP.

In addition to viral neutralization, humoral vaccine-elicited responses correlating with protection may further include functional mechanisms mediated by the fragment crystallizable (Fc)-domain of the antibody. Those include antibody-mediated cellular phagocytosis or killing, complement deposition or cellular activation mediated by Fc-receptors. Based on the available samples, these antigen-specific functionalities may be investigated by biophysical characterization using a multiplexed array and a series of functional assays commonly referred to as a systems serology approach. Further, the contribution of innate or inflammatory responses may be investigated through transcriptional profiling by RNA sequencing. Details of these analyses will be described in a separate SAP.

5.8.2.1. Parameters

The following humoral immune responses are measured by immunogenicity against the insert using humoral immune responses, including titers of neutralizing antibodies and S-ELISA titers, functional and molecular antibody characterization and RBD antibodies and N-ELISA positivity. Immunogenicity against the vector will be explored using an adenovirus neutralization assay to assess neutralizing antibody responses against the vector.

5.8.2.2. Handling of Missing and/or Unquantifiable Immune Response Data

Missing immune response data will not be imputed.

Values will be imputed based on the type of analysis. For the calculation of the geometric mean titer, values below LLOQ will be imputed to LLOQ/2. While for the calculation of the geometric mean of the increase from baseline, values below LLOQ will be imputed to LLOQ. The LLOQ values per assay are available in the data base.

Data above the ULOQ will be imputed with the ULOQ.

5.8.2.3. Immune Response Analysis

No formal hypothesis on immunogenicity will be tested.

5.8.2.4. Immunogenicity Against the Insert:

5.8.2.4.1. Humoral assays

For VNA (both wild-type virus and pseudovirion expressing S protein, as available) and S-ELISA assays following results will be calculated: N, geometric mean^a and corresponding 95% CI of the actual values and fold increases from baseline will be tabulated and graphically presented.

For the calculation of the geometric mean and its corresponding 95% CI, the arithmetic mean and its corresponding 95% CI are calculated on the log10 transformed values. These values are back transformed to provide the geometric mean and its corresponding 95% CI.

For wild type, pseudovirion VNA and S-ELISA separately:

- A sample will be considered positive if the value is strictly greater than the LLOQ ($>\text{LLOQ}$).
- Responder definition. A post-baseline sample will be considered a responder if at least one of the following conditions is satisfied:
 - The baseline sample value is less than or equal to the LLOQ ($\leq\text{LLOQ}$) and the post-baseline sample is strictly greater than the LLOQ ($>\text{LLOQ}$)
 - The baseline sample value is strictly greater than the LLOQ ($>\text{LLOQ}$) and the post-baseline sample value represents an at least 4-fold (≥ 4 -fold) increase from the baseline sample value.

Actual values are tabulated and shown as box plots with the corresponding geometric mean, 95% CI per time point and minimum and maximum are shown for each assay. For the immuno subset actual values are tabulated and shown as dot plots with dots for participant values, and the corresponding geometric mean and 95% CI per time point for each assay.

In addition, GMT plots over time, combining the regimens in one graph (without individual participant dots) will also be generated.

Participant profiles of the actual values over time will be graphically presented for Covid-19 cases.

Correlation plots between humoral assay results will be provided for selected time points.

In the graphs, original values will be displayed on the log¹⁰ scale.

^a calculate the mean and corresponding 95% CI of the log¹⁰ transformed values, back-transform this mean [i.e. 10^{mean}] and CI [i.e. 10^{CI}].

Further details may be provided in the DPS.

For the **N-ELISA** the proportion of participants that are positive will be tabulated.

5.8.2.5. Immunogenicity Against the Vector

For immunogenicity against the Ad26 vector backbone (Adenovirus neutralization by neutralization assay) following statistics will be calculated: geometric mean and corresponding 95% CI of the actual values, and number and percentage of participants with a positive sample.

Correlation plots with the Adeno assays versus the assays against the inserts will be provided for the most important time points.

5.8.2.6. SARS-CoV-2 viral genome sequence analysis

SARS-CoV-2 viral genome sequence analysis will be performed using Next Generation Sequencing (NGS) using the SWIFT Biosciences to evaluate the presence of polymorphisms and variations at the amino acid level.

Sequence results will be presented only for the spike protein and is focused on a predefined list of amino acid positions of interest. Data are transferred as the consensus sequence from the sample (i.e. no minority variants or mutation frequencies are transferred for this analysis). A separate virology report will be prepared.

Time Points and Samples

Samples for viral sequencing are taken throughout the T&E schedule. An attempt is made to sequence the sample closest to the onset of symptoms, but sequencing is triggered at the discretion of the virologist considering the SARS-CoV-2 viral load levels and the limitations of the sequencing assays.

Definitions

Polymorphisms, ie genetic variations, are defined as amino acid changes from the SARS-CoV-2 Wuhan-Hu1 Reference Sequence.

Wild type: If at certain position the amino acid in the participant sequence matches the reference sequence, that is no genetic variation is present at that position, the virus is considered to be wild type at that position.

Parameters to Analyze

The following parameters will be analyzed:

Number (%) of participants with a SARS-CoV-2 variant with a specific substitution (“amino acid level”, see below).

Number (%) of participants with a SARS-CoV-2 variant with a specific substitution profile (“variants”, see below)

Positions & Genetic Variations of Interest

Amino acid level:

In the SARS-CoV-2 spike protein, based on changes in the N-terminal or receptor binding domains, and changes observed in naturally occurring variants

- S13I, L18F, T20N, P26S, 69del + 70del, D80A, L98F, D138Y, Y144del, W152C, R190S, D215G, L242H, 242del + 243del + 244del, R246I, K417N, K417T, N439K, V445A, L452R, Y453F, S477N, S477R, E484K, N501Y, A520S, A570D, D614G, H655Y, P681H, A701V, T761I, S982A, T1027I, D1118H

Variants (lineage-WHO label-defining mutations):

- B.1.1.7 – Alpha - H69del, V70del, Y144del, N501Y, A570D, D614G, P681H, T716I, S982A, D1118H
- B.1.351 – Beta – K417N, E484K, N501Y, D614G, A701V
- B.1.617.2/AY.1/AY.2 – Delta – L452R, T478K, D614G, P681R
- B.1.427/429 – Epsilon – W152C, L452R, D614G
- B.1.525 - Eta - A67V, H69del, V70del, Y144del, E484K, D614G, Q677H, F888L
- P.1 – Gamma - K417T, E484K, N501Y, D614G, H655Y
- B.1.526 – Iota - L5F, T95I, D253G, D614G, E484K, A701V
- B.1.617.1 – Kappa - G142D, E154K, L452R, E484Q, D614G, P681R
- C.37 – Lambda - R246del, S247del, Y248del, L249del, T250del, P251del, G252del, D253N, L452Q, F490S, D614G, T859N
- P.3 – Theta - L141del, G142del, V143del, A243del, L244del, E484K, N501Y, D614G, P681H, E1092K, H1101Y, V1176F
- P.2 – Zeta - E484K, D614G, V1176F (and not P.1, not P.3)
- B.1.621 - T95I, Y144T, Y145S, ins145N, R346K, E484K, N501Y, D614G, P681H, D950N
- C.36.3 - W152R, R346S, L452R, D614G, Q677H, A899S
- R.1 - W152L, E484K, D614G, G769V
- B.1.1.519 - T478K, D614G, P681H, T732A
- B.1/B.1.2/B.1.1/B.1.1.214 - D614G (not any other variant)

Additional variants may be added depending upon the epidemiology of SARS-CoV-2 infection.

Analysis Methods

Frequencies and percentages will be presented for the specified parameters. The denominator is the number of subjects with a COVID-19 episode with sequencing data. Summaries will be provided by subgroup and intervention arm.

5.8.3. Definition of Subgroups

Selected safety and efficacy analyses will be summarized by treatment group for the following subgroups:

- sex
- race
- ethnicity
- age categories 1 (18-≤59, ≥60years)
- age categories 2 (18-<40, 40-≤59, ≥60 years)
- age categories 3 (18-<40, 40-≤59, 60-≤69, 70-≤79, ≥80 years)
- age categories 4 (18-≤64, ≥65years)
- age categories 5 (≥75years)
- country
- region (South-Africa, US, Latin-America, Europe (if applicable), Asia (if applicable)). Regions may be modified/pooled based on participation.
- presence of baseline comorbidity
- baseline seropositivity status (positive vs. negative)
- frailty index (frail, pre-frail, non-frail, unknown, see appendix [6.9](#))
- in subjects with a baseline PCR+ test result (Day 1)
- in subject with a baseline PCR+ test result (Day 1) OR are baseline seropositive
- baseline VNA Ad26. Status (responder/nonresponder)

If necessary, for country approval/submission, an analysis by country or country*subgroup interactions may be added.

5.8.4. Patient-Reported Outcomes

5.8.4.1. Symptoms of Infection with Coronavirus-19 (SIC)

The SIC is a disease-specific patient-reported outcome (PRO) instrument that is completed by the participant, self-administered. The SIC has a total of 30 items assessing signs and symptoms of COVID-19. The first 25 items, the participant indicates “yes” or “no” if they have a symptom and if “yes” report a severity from 0 (none) to 10 (worst possible). The second part has the participant enter their temperature, and the third part has the participant record “yes” or “no” (absence or presence of additional signs and symptoms). The analyses are conducted in two ways, by part 1, part 2 and part 3, scored separately, and also grouped into related categories for composite scoring :

SIC Analysis Approach One:

- Part 1 (25 symptoms): Each symptom is present or absent (0), and if present rated on a 10 point scale from ranging from 0 (None) to 10 (Worst possible).

The **symptom score** is the mean score of all items on the SIC for each day, during the COVID-19 episode.

The **symptom duration** is the period from the first day of symptoms till the last day with symptoms in Days (calculated as last day with symptoms – first day of symptoms + 1).

The **symptom AUC** is the area under the curve for the complete COVID-19 episode.

The **peak symptom score** is the maximum of all the symptom scores during the COVID-19 episode.

- Part 2: Fever/ temperature.

Fever will be scored (fever score) as the maximum recorded temperature for each day during the COVID-19 episode.

Fever will be coded as ‘Present’ if the fever score is $\geq 38.0\text{ }^{\circ}\text{C}$ or $\geq 100.4\text{ }^{\circ}\text{F}$ and ‘Absent’ otherwise.

The **total fever days** is the number of days with fever present during the COVID-19 episode.

Fever duration will be the period from the first day with fever till the last day with fever in Days (calculated as last day with fever – first day of fever + 1).

The **peak fever** is the maximum fever score during the COVID-19 episode.

The **fever AUC** is the AUC of fever score during the total of fever days of the COVID-19 episode. (For the AUC if there is a single missing day between days with fever the missing day will be ignored, i.e., interpolation will be used in the calculation of the AUC.)

The fever score will also be coded using FDA grades for fever.

Part 3: Each of the 3 specific symptoms is either present (1) or absent (2).

The **specific symptom score** is the mean of all scores during the COVID-19 episode.

The **specific symptom duration** is the duration of specific symptoms during the COVID-19 episode from the first day with a specific symptom till the last day with a specific symptom in Days (calculated as last day with a specific symptom – first day of a specific symptom + 1).

The **total specific reported symptom score** is the mean of all scores during the COVID-19 episode at which a subject has reported at least one specific symptom.

Note 1: For Part 1, total scores will be calculated based on the number of assessments completed by the participant per day and in cases where more than 75% of the items needed to calculate the score is not collected (reported as no answer to the part 1 Yes/No possibility AND no severity rate), then the value for that score will be set to missing. For example, if a participant has responded to 7 or more out of the 25 symptom scale questions the score will be the mean of the available questions. If the participant has only completed 6 or less of the questions then the symptom score will be set to missing, unless a subject has only provided responses ‘Yes’ to all of the answered

questions (then it is assumed that the subject only noted the pertinent symptoms for that day). In case of missing severity rate and the answer was ‘yes’ the rate will be imputed by ‘5’.

SIC Analysis Approach Two: Composite Scoring

For the purpose of computing the SIC composite scores, the 25 SIC symptom items with severity ratings (part 1) are scored such that item scores range from 0 (“No,” i.e., not experienced; or “None”) to 10 (“Worst possible”). Except for the Sensory score, SIC composite scores are computed as the average of the symptom severity ratings for each set of items (Constitutional [where C7 = 0 if NO, 10 if YES], Gastrointestinal, Musculoskeletal, Neurological, Respiratory, Upper Respiratory, Lower Respiratory). The average composite score is a number between 0 and 10 (inclusive). Because all SIC composite scores are in the same metric as the item-level severity ratings, this links the interpretation of the SIC composite scores to the items, with higher scores reflecting worse symptoms.

Constitutional. The SIC includes 7 Constitutional items, 2 of those items use a dichotomous response scale (C6: Fever, C7: Uncontrollable body shaking/shivering). The constitutional score includes C7 as well as the 5 Constitutional items that use the 11-point severity rating scale (C1: Feeling generally unwell, C2: Fatigue (tiredness), C3: Chills, C4: Skin rash, C5: Eye irritation/discharge). To allow scoring in the 0-10 item metric, a “Yes” to C7 was re-coded to a value of 10 given the severe nature of rigors. The SIC Constitutional score is the equally weighted average of 6 Constitutional items (excluding C6). Fever as described above is analyzed on its own (part 2 of SIC Analysis Approach1):

Constitutional = average of (C1, C2, C3, C4, C5, C7) where C7 = 0 if NO, 10 if YES

Gastrointestinal. The SIC Gastrointestinal score is an equally weighted average of the severity ratings of all 5 SIC items related to Gastrointestinal symptoms (G1: Diarrhea, G2: Vomiting, G3: Nausea, G4: Abdominal/stomach pain, G5: Loss of appetite):

Gastrointestinal = average of (G1, G2, G3, G4, G5)

Musculoskeletal. The SIC Musculoskeletal score is an equally weighted average severity ratings of 3 items (M1: Physical weakness, M2: Muscle aches/pains, M3: Joint aches/pains):

Musculoskeletal = average of (M1, M2, M3)

Neurological. The SIC Neurological score is an equally weighted average severity ratings of 3 items (N1: Headache, N2: Feeling faint, N3: Problems thinking clearly/brain fog):

Neurological = average of (N1, N2, N3)

Sensory. Two SIC items (N4: Decreased sense of smell, N5: Decreased sense of taste) are a 2-item Sensory composite score with 3 possible values:

Sensory = 0 if NO to both N4: Decreased sense of smell and N5: Decreased sense of taste
 = 5 if YES to only one of the 2 items (and NO to the other item)
 = 10 if YES to both items

Respiratory. The SIC Respiratory score is an equally weighted average severity rating of all 9 Respiratory items (R1: Cough, R2: Shortness of breath, R3: Sore throat, R4: Nasal congestion, R5: Wheezing, R6: Runny nose, R7: Sneezing, R8: Chest congestion, R9: Chest pain/pressure/tightness):

Respiratory = average of (R1, R2, R3, R4, R5, R6, R7, R8, R9)

In addition, separate Lower Respiratory and Upper Respiratory SIC scores were computed:

Lower Respiratory = average of (R1, R2, R5, R8, R9)

Upper Respiratory = average of (R3, R4, R6, R7)

For each composite the following analysis will be conducted:

The **<Composite name> symptom score** is the mean of all scores for each day, during the COVID-19 episode.

The **<Composite name> symptom duration** is the period from the first day of symptoms till the last day with symptoms in Days (calculated as last day with symptoms – first day of symptoms + 1).

The **<Composite name> symptom AUC** is the area under the curve for the complete COVID-19 episode.

The **<Composite name> peak symptom score** is the maximum of all the symptom scores during the COVID-19 episode.

After completing the SIC, each day the participant completed a Patient Global Assessment of Severity, asking them to rate the severity of their symptoms in the last 24 hrs with responses of “No Symptoms”, “Mild”, “Moderate” or “Severe”

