6.6. Appendix 6 FDA Toxicity Grading Scale for Vaccine Trials

Adapted from the FDA Guidance document “Toxicity Grading Scale for Healthy Adult and Adolescent Volunteers Enrolled in Preventive Vaccine Clinical Trials” (September 2007)

Local Reaction to Injectable Product	Mild (Grade 1)	Moderate (Grade 2)	Severe (Grade 3)	Potentially Life Threatening (Grade 4)
Pain/Tenderness [#]	Aware of symptoms but easily tolerated; Does not interfere with activity; Discomfort only to touch	Notable symptoms; Requires modification in activity or use of medications; Discomfort with movement	Incapacitating symptoms; Inability to do work, school, or usual activities; Use of narcotic pain reliever	Hospitalization; Pain/tenderness causing inability to perform basic self-care function
Erythema [#]	25 – 50 mm	51 – 100 mm	>100 mm	Hospitalization; Necrosis or exfoliative dermatitis
Swelling [#]	25 – 50 mm	51 – 100 mm	>100 mm	Hospitalization; Necrosis

[#] Revised by the sponsor.

Vital Signs *	Mild (Grade 1)	Moderate (Grade 2)	Severe (Grade 3)	Potentially Life Threatening (Grade 4)
Fever (°C) ** (°F)**	38.0 - 38.4 100.4 - 101.1	38.5 - 38.9 101.2 - 102.0	39.0 - 40.0 102.1 - 104.0	>40 >104.0
Tachycardia - beats per minute	101 – 115	116 – 130	>130	Hospitalization for arrhythmia [#]
Bradycardia - beats per minute***	50 – 54	45 – 49	<45	Hospitalization for arrhythmia [#]
Hypertension (systolic) - mm Hg	141 – 150	151 – 155	>155	Hospitalization for malignant hypertension [#]
Hypertension (diastolic) - mm Hg	91 – 95	96 – 100	>100	Hospitalization for malignant hypertension [#]
Hypotension (systolic) – mm Hg	85 – 89	80 – 84	<80	Hospitalization for hypotensive shock [#]
Respiratory Rate – breaths per minute	17 – 20	21 – 25	>25	Intubation

* Participant should be at rest for all vital sign measurements.

** For oral temperature: no recent hot or cold beverages or smoking.

*** When resting heart rate is between 60 – 100 beats per minute. Use clinical judgement when characterizing bradycardia among some healthy participant populations, for example, conditioned athletes.

[#] Revised by the sponsor.

Statistical Analysis Plan VAC31518COV3001

Systemic (General)	Mild (Grade 1)	Moderate (Grade 2)	Severe (Grade 3)	Potentially Life Threatening (Grade 4)
Vomiting [#]	No interference with activity or 1 – 2 episodes/24 hours	Some interference with activity or >2 episodes/24 hours	Prevents daily activity, requires outpatient IV hydration	Hospitalization; Hypotensive shock

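### Fever AUC is taken over absolute temperature, so it nearly repeats the count of fever days and adds almost nothing on fever height

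*SAP*

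**What the plan says.** SAP section 5.8.4.1, Part 2, sets out the fever statistics for a COVID-19 episode:

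- The score: "Fever will be scored (fever score) as the maximum recorded temperature for each day during the COVID-19 episode". A day counts as a fever day when this score reaches 38.0 °C (100.4 °F).
- Total fever days "is the number of days with fever present during the COVID-19 episode". Fever duration, from first to last fever day, is listed as well.
- Peak fever "is the maximum fever score during the COVID-19 episode".
- Fever AUC "is the AUC of fever score during the total of fever days of the COVID-19 episode". A single missing day between fever days is bridged by interpolation.
- Grading: "The fever score will also be coded using FDA grades for fever".

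No reference temperature is subtracted for the AUC, nothing is divided by the number of days, and no integration rule or unit is named. The only AUC formula written out in the SAP is the trapezoid for viral load in section 5.5.3.

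Section 5.6.1.3 compares the section 5.8.4 scores between vaccine and placebo among infected participants, to judge whether the vaccine reduces severity. The composite scoring in 5.8.4.1 leaves fever out of the Constitutional score and refers it back to Part 2.

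**The concern.** An area under a curve combines height and duration sensibly when zero on the scale means that the symptom is absent. The SIC symptom items have that property, since they run from 0 for none to 10, and so the symptom AUC works. Body temperature does not. Measured from 0 °C, every fever day contributes at least 38 units before any account is taken of how high the fever was.

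Two arms could have the same number of fever days and clearly different temperatures, and their fever AUCs would be almost equal. A reader who takes fever AUC as a measure of overall fever burden could then report no effect on burden when the statistic had little chance of showing one. Total fever days already gives the information that fever AUC would carry.

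**Working it through.** The SAP states no numerical result for fever AUC, so there is no figure to reproduce. The check applies the definition as written.

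**Inputs from the SAP.** The lower limit of the score on a fever day is 38.0 °C (section 5.8.4.1). The top of grade 3 is 40.0 °C (Appendix 6, whose grade 3 fever entry reads "39.0 - 40.0 102.1 - 104.0"). Grade 4 lies above 40 °C, and 41 °C is used below as an example.

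**Range of the score.**

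- 38 to 40 °C: (40 − 38)/38 = 5.3%.
- 38 to 41 °C: (41 − 38)/38 = 7.9%.
- In Fahrenheit, 100.4 to 104.0: 3.6/100.4 = 3.6%.

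**Height against days, at constant temperature T for d days.** The integration rule is not stated, so both are shown: daily sum = d × T; trapezoid = (d − 1) × T.

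| Episode | Daily sum | Trapezoid |
|---|---|---|
| 5 days at 38.0 °C | 190 | 152 |
| 5 days at 40.0 °C | 200 (+5.3%) | 160 (+5.3%) |
| 6 days at 38.0 °C | 228 (+20%) | 190 (+25%) |
| 3 days at 40.0 °C | 120 | 80 |
| 4 days at 38.0 °C | 152 | 114 |

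Percentages are relative to five days at 38.0 °C. The last two rows show that one more day at the threshold outweighs the whole range from 38.0 to 40.0 °C. Under the trapezoid, a one-day fever has d − 1 = 0 and scores 0 at any temperature.

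**Collinearity with total fever days.** The SAP gives no distribution of fever days or temperatures, so these are assumptions.

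- Days uniform on 1 to 3, 5, 7 or 10, temperature uniform on 38–40 °C, daily sum: R² of AUC on number of days is 0.998 to 0.999 in every case.
- Days 1 + Poisson(2), mean excess over 38 °C about 0.8 °C: R² is 0.999 under either rule, and R² on the episode's mean temperature is about 0.0005.

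**A pure difference in height.** In the second scenario, halve the excess over 38 °C and leave days unchanged. Mean temperature falls from 38.81 to 38.40 °C.

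- Relative change in mean AUC: 0.41/38.81 = 1.1%.
- Absolute change with a mean of 3 fever days, daily sum: 3 × 0.41 = 1.2 units.
- SD of the AUC, almost all from days (variance 2): 38.6 × √2 ≈ 54.6.
- Standardised difference: 1.2/54.6 ≈ 0.02.

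Simulation with 20,000 per arm gave 0.03 (daily sum) and 0.01 (trapezoid), which agrees within its standard error of √(2/20,000) = 0.01. Peak fever in the same simulation had a standardised difference of about 1.1.

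**With a reference subtracted** (same scenario, daily sum, references for illustration only):

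| Reference | R² on days | Mean AUC | Standardised difference |
|---|---|---|---|
| none | 0.999 | falls about 1% | about 0.02 |
| 37 °C | 0.67 | 5.40 to 4.22 (−22%) | 0.44 |
| 38 °C | 0.29 | 2.41 to 1.23 (−49%) | 0.70 |

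**The case against.** The strongest reply is that the plan does not rely on fever AUC for intensity. Section 5.8.4.1 has peak fever and the FDA grades, and section 5.7.2 summarises temperature over time from symptom onset in COVID-19 cases. A reader might infer from the AUC definition that the trial could not see an effect on fever height. The documents do not support that, and this part of the reply stands in full.

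Other points that stand, in whole or in part:

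- The SAP never says that fever AUC must reflect height and duration together. Section 5.6.1.3 asks only that the set of scores cover presence, severity and duration. That limits the criticism to redundancy: a statistic listed beside total fever days should add something to it.
- The zero for a one-day fever and the 25% for a sixth day depend on the trapezoid, which the SAP gives only for viral load. By daily sum, a one-day fever scores its temperature and the sixth day adds 20%. The main conclusion is the same under both rules.
- Fever AUC and total fever days are not identical. A bridged missing day enters the first but has no recorded fever to enter the second.
- Thresholds are given in equivalent Celsius and Fahrenheit values, and conversion to one unit is routine. Nothing suggests that units would be mixed, so this is a detail to write down and no defect in itself.
- Any reference temperature is partly arbitrary, and the AUC would still depend on days.

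None of this removes the central fact that the quantity integrated varies by only about 5% between 38 and 40 °C.

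**Conclusion.** The point holds as a small, inexpensive improvement. As defined, fever AUC is close to a rescaled count of fever days. Raising every fever day from 38 to 40 °C changes it by about 5% (about 8% at 41 °C), against 20% or 25% for a sixth day. This follows from the stated threshold and the range of fever temperatures. Only the R² values and standardised differences rest on assumed distributions, and the near-collinearity held in every scenario tried.

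The consequence is confined to one exploratory statistic, summarised descriptively under section 5.8.4.2. It has no allocated alpha and no link to the co-primary or confirmatory secondary endpoints. It would go too far to say that fever AUC cannot move with temperature, since it does move slightly, or that the plan lacks a measure of fever intensity.

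**What to change.** In section 5.8.4.1, Part 2, redefine fever AUC as the sum over fever days of (daily maximum temperature − reference), one day per step, with all values in one stated unit. Name the reference temperature and record it before fever AUC is tabulated by arm, because the result depends on it. It is a scoring constant and leaves the fever threshold unchanged. With a reference of exactly 38.0 °C, a fever day at the threshold would score 0; a lower reference avoids this but leaves more weight on days. State that a bridged missing day enters the sum with its interpolated value. The daily sum is preferable to the trapezoid because a one-day fever then does not automatically score 0.

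The cost is a few lines of definition and a small programming change, with no new data. The downside is that the reference is somewhat arbitrary and the AUC will still depend partly on the number of days, so total fever days and peak fever should continue to be shown beside it.
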